4.3.1 Inclusion Criteria

- Preterm infants whose mothers are resident within the north west neonatal network, born between 25+0 to 31+6 weeks gestational age

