4.3.2 Exclusion Criteria

- Major congenital or life threatening abnormalities or congenital abnormalities that preclude early milk feeding
- Inability to randomise infant within 48 hours
- Infants less than 25+0 weeks or more than 31+6 weeks

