4.4 Screening and enrolment

For part one of the study, we plan to randomise all eligible infants, unless explicitly requested by the parents for their baby not to take part. Where possible parents will be approached before delivery, and the study explained to them eg for mothers at risk of premature delivery. In all cases, the study will be explained to the parents by one of the clinical team or study investigators shortly after birth, and a written parent information leaflet (PIL pt 1) will be given to the parents. This process will be documented in the infant's medical notes by the person explaining the study, with a confirmation sticker. Randomisation to one of the three feeding arms will take place between 24-48hrs of age.

[figure not shown]
For part two of the study, parents will be approached by one of the clinical team or the study investigators after 48hrs of age, and part two of the study will be explained to them, with a written parent information leaflet (PIL pt 2) given to them. At a convenient time for the parents, informed consent will then be sought for part 2 of the study. All infants will be recruited from the Chelsea and Westminster Hospital Neonatal Unit.

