4.6 Randomisation

Randomisation will be generated centrally using a computer program, with minimisation by infant sex, gestational age (25-27+6 wks, 28-31+6 wks) birth-weight Z score (<-1.28, >-1.28) Randomisation will take place between 24-48hrs of age. Infants will be randomised to receive either HDM or PTF to make up any shortfall in Mother's Own Milk (MOM) until 34+6 weeks postmenstrual age. Blinding of the intervention is not practicable because of the distinctive appearances of human milk and formula, and the method of administration to preterm babies by syringe and nasogastric tube. At 35 weeks, the infant will be close to discharge, and feeding will be directly from the breast or formula by bottle in accordance with maternal choice.

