4.11.2 Statistical analysis

Outcomes will be analysed both for by intention to treat and as per protocol using multiple linear regression with adjustment for covariates where appropriate. Baseline covariates such as gender, gestational age, and birthweight z score, will be controlled for by randomisation stratification, while those such as ethnicity will be adjusted for. To address the null hypothesis differences between groups will be tested using ANOVA, with examination of the 3 pairwise differences for magnitude of differences. For the purposes of modelling randomised babies will be assigned to categories of overall intake (predominantly MOM, predominantly PTF, predominantly HDM). Results will be presented as estimates and 95% confidence intervals for differences in means.

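### Multiples can be enrolled, but the plan has no sibling allocation rule and its ANOVA treats siblings as independent, so its standard errors are miscalibrated in a direction set by how siblings are allocated

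*Combined protocol and SAP*

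**What the plan says.** Section 4.4 sets the enrolment policy for part one: "we plan to randomise all eligible infants, unless explicitly requested by the parents for their baby not to take part". The inclusion criterion in 4.3.1 is "Preterm infants whose mothers are resident within the north west neonatal network, born between 25+0 to 31+6 weeks gestational age". The exclusions in 4.3.2 are major abnormalities, failure to randomise within 48 hours, and gestation outside the range. Neither list mentions singleton or multiple birth.

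Section 4.6 allocates each infant centrally, "with minimisation by infant sex, gestational age (25-27+6 wks, 28-31+6 wks) birth-weight Z score". It does not say whether siblings are allocated together or one by one, and multiple birth is not a minimisation factor.

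Section 4.11.2 says outcomes will be analysed "using multiple linear regression with adjustment for covariates where appropriate". For the null hypothesis on adiposity, "differences between groups will be tested using ANOVA", with the three pairwise contrasts looked at for their size and results reported with 95% confidence intervals. It gives no random effect, robust variance or one-infant-per-family rule. The sample size in 4.11.1 has no design effect. The randomisation and baseline fields in 4.9.3 and 4.9.4 have no multiple-birth item or family identifier, although they do include the infant's date and time of birth and the mother's date of birth.

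**The concern.** A population born before 32 weeks with no exclusion of multiples can be expected to include twins and some triplets. Siblings share a mother, a gestation, genes and one supply of mother's own milk. That supply determines how much donor milk or formula each receives, so siblings are linked through the trial's own exposure as well as through biology. Their adiposity is likely to be correlated.

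ANOVA and ordinary regression assume independent infants. With correlated siblings, the stated standard error is too small if siblings sit in the same arm and too large if they are mostly in different arms. What is at stake is the calibration of the test and intervals for the primary outcome. The effect estimate and its interval are also what the pilot would pass on to the planned trial of about 4000 babies.

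**Working it through.** **1. The plan's own figure.** Inputs from 4.11.1: SD 0.243 l, difference 0.243 l, 22 infants per arm, 5% significance. Table 3 uses a Bonferroni correction, taken here as three two-sided comparisons (0.05/3 = 0.0167).

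- Power = Φ(1/√(2/22) − 2.394) = Φ(3.317 − 2.394) = 82.2%. With alpha rounded to 0.017 it is 82.4%, the figure in Table 3.
- Recruitment: 22/0.80 = 27.5, rounded up to 28 per arm, as stated.

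Both figures treat infants as independent.

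**2. Effect of twins on a pairwise difference.** Let q be the share of infants who are twins, ρ the within-pair correlation, and s the chance that both twins are in the same arm. With three equal arms of n infants:

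- Var(difference) = (2σ²/n) × D, where D = 1 + qρ(3s − 1)/2.
- Always together (s = 1): D = 1 + qρ.
- Fully independent allocation (s = 1/3): D = 1.
- Always apart (s = 0): D = 1 − qρ/2.

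The ratio of true to ANOVA standard error is approximately √D.

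**3. Numbers.** q and ρ are assumptions, not document figures: q = 0.2-0.4, ρ = 0.3-0.7. So qρ runs from 0.06 to 0.28.

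| Siblings | D | √D | Pairwise error at nominal 5% |
|---|---|---|---|
| Together | 1.06 to 1.28 | 1.03 to 1.13 | 5.7% to 8.3% |
| Independent | 1.00 | 1.00 | 5.0% |
| 90% of pairs split (s = 0.10) | 0.98 to 0.90 | 0.99 to 0.95 | 4.8% to 3.9% |
| Always apart | 0.97 to 0.86 | 0.98 to 0.93 | 4.7% to 3.5% |

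The error column is 2 × [1 − Φ(1.96/√D)].

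**4. Simulation of the overall ANOVA** (66 infants, three arms, no true difference, nominal 5%).

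- Siblings together: several runs over the assumed ranges gave type I error of about 6-10% and true/ANOVA SE of about 1.02-1.15.
- Each twin minimised separately on the three factors in 4.6, with assumed factor frequencies and either deterministic or 80% biased assignment: about 83-90% of pairs were split. Type I error was about 3-5%, and the SE ratio was mostly 0.93-1.00. At 0.93 the ANOVA interval is 1/0.93 = 1.075 times as wide as it should be, or about 7% too wide.

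**5. Power and size if siblings share an arm.** At 22 per arm, power is Φ(3.317/√D − 2.394): 79.6% at D = 1.06 and 70.5% at D = 1.28, against 82.2%. The analysable number needed is 22 × D = 23.3 to 28.2, so 24 to 29 per arm.

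**The case against.** A reader might infer that the planned ANOVA gives too many false positives. The documents do not support that. Inflation arises only if siblings share an arm, and nothing says they do. Section 4.6 minimises on infant-level factors, which tends to separate twins, and the error rate is then at or below 5%. Nor are the standard errors wrong in every case: under fully independent allocation of each twin they are right on average. This stands, and it limits the point to miscalibration whose direction depends on a rule that is not stated.

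It is also fair to say that this is a feasibility pilot which describes itself as likely underpowered, and that a shift of a few percent in a standard error would change little. That keeps the point moderate. But the trial does test a null hypothesis and reports intervals meant to inform a larger trial. Splitting by minimisation also offers no assurance for the planned intake-category model: siblings whose mother has ample milk could both be classed as predominantly mother's own milk, whatever their arms.

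Two further objections have force. With 66 scans and 20-40% twins there are only about 7 to 13 pairs, so the variance for mother is poorly estimated. In simulation, a random intercept without a small-sample correction rejected about 7-8% of the time when most pairs were split. And siblings could probably be identified from the birth dates already collected, so a new field is a safeguard more than a necessity.

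The flowchart is not reproduced in the text available and some pages were removed, so a sibling rule stated only there cannot be ruled out.

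**Conclusion.** The point holds in conditional form. Multiples are eligible, no sibling allocation rule is stated, and the analysis treats siblings as independent. If siblings are kept together, the true standard error is about 2-15% larger than reported and type I error is about 6-10%. If each infant is minimised individually, which is the natural reading of 4.6, type I error is about 3-5%, intervals are up to about 7% too wide, and precision is lost when the correlation is high.

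All of these sizes rest on assumed values: 20-40% of scanned infants are twins, within-pair correlation is 0.3-0.7, higher-order multiples are ignored, and the minimisation factor frequencies are assumed. The change should be made because it is cheap and gives better-calibrated inference, not because the written plan has been shown to inflate false positives.

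**What to change.** - **Section 4.11.2:** fit the same linear model with a random intercept for mother and a small-sample correction such as Kenward-Roger, or use cluster-robust standard errors by mother with a small-sample correction. The correction is needed for either option. Apply the same approach to the intake-category model.
- **Section 4.6:** state whether siblings are allocated together or individually. If together, carry the design effect into 4.11.1.
- **Sections 4.9.3 and 4.9.4:** record multiple birth or a maternal identifier on the case report form. The pilot could then also give the larger trial its share of multiples and a rough within-pair correlation.

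The cost is one model term, one sentence and one form field. The drawbacks are that the variance for mother rests on few sibling pairs, so an uncorrected mixed model would be anti-conservative, and that intervals would be slightly wider if siblings share an arm.

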- 2) the secondary outcomes of
 - Regional adiposity, as measured by whole body MRI
 - Non adipose tissue, as measured by whole body MRI
 - Total brain volume, as measured by MRI
 - Anthropometry (weight, length, and head circumference)
 - IHCL, as measured by magnetic resonance spectroscopy
 - blood pressure
 - Stool and urine metabolomic profile
 - Blood Quantitative Insulin Sensitivity Check Index (QUICKI) – at discharge only between infants randomised to receive fortified MOM+/-HDM, unfortified MOM+/- HDM or MOM+/-PTF.

C: By using HDM with known macronutrient content, we aim to correlate macronutrient intake of each intervention with the above outcomes.

4. Methods

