4.8.5 Unfortified Human Milk

For infants randomised to receive unfortified human milk the instruction to only use unfortified HDM to supplement unfortified MOM will be made on the infants feeding plan. For these infants, the situation may arise where the growth of the infants is deemed suboptimal by the clinical team. Therefore, weight gain will be assessed two weeks after a milk volume of 120ml/kg/d has been reached. At this point, if the infant has crossed down 3 centile bandwidths from birthweight centile bandwidth, or shows continued downward crossing if less than the 0.4th centile, using birthweight centile charts, then the

infant will discontinue the feeding intervention. There may be other causes of poor weight gain than inadequate enteral nutrition. These include for example, respiratory distress syndrome, infection, chronic lung disease, gastro-oesophageal reflux disease, anaemia, patent ductus arteriosus, or underlying congenital anomaly. Once these causes have been excluded or corrected, and the weight loss has been confirmed from at least two weights over a 72 hour period, fortification will be commenced. Infants will then receive fortified HDM, and undergo all outcome measures. Analysis will be as per protocol, and also for categories of overall intake (see statistical analysis).

This three centile drop cut off value is based on results of a longitudinal preterm growth reference by Cole et al (submitted). This is a study of routinely collected growth data (co-ordinated by the Neonatal Data Analysis Unit) from 113 neonatal units across the UK from 2006-2011. A growth reference for weight, length, and head circumference in preterm infants less than 32 weeks from birth to term/near term was constructed, stratified for birth gestation week, and compared to currently used birthweight centile charts. In this comparison, average growth curves for all infants by week of birth gestation, crossed down 2-3 birthweight centile bandwidths over a period of 3-4 weeks from birth, before becoming parallel to the birthweight centile bandwidth curves. Time taken to reach full milk feeds will vary depending on feeding tolerance, but typically will take from a few days to a couple of weeks. A period of two weeks after full milk feeding (120ml/kg/d and above) has been reached, is therefore expected to coincide with no further crossing down in birthweight centile bandwidth curves.

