4.9.3 Randomisation

- Study number
- Date and time of birth
- Gender
- Confirmation of eligibility (full eligibility check)
- Date of parental consent
- Name of person taking consent
- Gestational age (in weeks and days)
- Recruiting hospital
- Allocated trial intervention (HDM or PTF)

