4.9.5 Daily evaluations

Performed daily until discharge from NICU

- Record nutritional intake (parenteral nutrition, daily volume of MOM, daily volume of trial feed – all collected on case report form)
- Record level of care (BAPM 2001 criteria)
- Record if infant is nil by mouth and reason for this (collected on case report form)
- Record of withdrawal information (collected on case report form)
- Weight (when on parenteral nutrition)

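### The milk-source intake categories in 4.11.2 cannot show a switch to fortifier, and no listed CRF item records fortifier, so Aim C protein could be understated in fortified infants

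*Combined protocol and SAP*

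**What the plan says.** **The switch.** Section 4.8.5 describes infants in the unfortified arm who meet a growth criterion and, after other causes are dealt with, start fortification: "Infants will then receive fortified HDM, and undergo all outcome measures". It then sends them to two analyses: "Analysis will be as per protocol, and also for categories of overall intake (see statistical analysis".

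**The categories.** The cross-reference leads to 4.11.2: "randomised babies will be assigned to categories of overall intake (predominantly MOM, predominantly PTF, predominantly HDM". No threshold is given for when one milk predominates. The same section plans ITT and per-protocol regression, and an ANOVA with the three pairwise arm differences. It does not define the per-protocol set.

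**The data.** The daily CRF items in 4.9.5 include "Record nutritional intake (parenteral nutrition, daily volume of MOM, daily volume of trial feed – all collected on case report form" and "Record of withdrawal information (collected on case report form". The content of the withdrawal item is not described. The randomisation data in 4.9.3 include "Allocated trial intervention (HDM or PTF", although the trial has three arms. Under 4.8.3, HDM composition is measured at the milk bank and printed on the bottle, so it describes the milk as supplied, before any fortifier.

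**The aim that uses these data.** Aim C in section 3 states: "we aim to correlate macronutrient intake of each intervention with the above outcomes".

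**The fortifier.** Section 4.8.4 fixes the rate at two sachets per 100 ml. Fortification starts at an enteral intake of 100 ml/kg/day in 4.8.2, but at 150 ml/kg/d in 4.8.4 and in the protocol summary.

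**The concern.** Section 4.8.5 gives the category analysis a specific job: to describe infants whose actual feed departed from their allocation because fortifier was added. Categories based only on milk source cannot do this. An infant fed mainly donor milk is *predominantly HDM* both before and after the switch.

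The same categories merge the fortified and unfortified HDM arms. *Predominantly MOM* can draw infants from all three arms. Yet section 2.2.2 says the trial is meant to begin separating the bioactive properties of human milk from slower early growth, by comparing fortified and unfortified HDM with PTF. The category model averages over that contrast.

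The data list adds to the problem. With no fortifier item and a two-level allocation field, intake built from the listed volumes and bottle labels alone would give fortified and unfortified infants the same protein and energy for the same volume. Aim C depends on that intake. Exposure that is not recorded during the stay may not be recoverable later.

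**Working it through.** **Inputs (Table 1, section 4.8.7, per 180 ml for a 1 kg infant)**

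| | MOM | HDM | Fortified MOM | Fortified HDM | Nutriprem 1 |
|---|---|---|---|---|---|
| Protein (g) | 2.7 | 2.2 | 4.7 | 4.4 | 4.7 |
| Energy (kcal) | 117 | 117 | 144 | 144 | 144 |

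**1. Check the table.** Protein/energy ratio = 100 × protein / energy. This gives 2.31, 1.88, 3.26, 3.06 and 3.26, against the stated 2.3, 1.9, 3.3, 3.1 and 3.3. The protein and energy rows are consistent with the stated ratios.

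**2. Spread within and between categories (protein).**
- Within *predominantly HDM*: 4.4 − 2.2 = 2.2 g.
- Within *predominantly MOM*: 4.7 − 2.7 = 2.0 g.
- Fortified HDM against PTF: 4.7 − 4.4 = 0.3 g.
- Unfortified HDM against PTF: 4.7 − 2.2 = 2.5 g.

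The spread inside the HDM category is nearly as large as the widest gap between HDM and PTF. If half the milk in the category were fortified (an assumption), its mean protein would be (2.2 + 4.4)/2 = 3.3 g, midway between two very different feeds.

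**3. Share of milk protein missed if fortifier is not counted.** Share = (fortified − unfortified) / fortified.
- All fortified HDM: 2.2/4.4 = 50% (48% to 52% allowing for one-decimal rounding).
- All fortified MOM: 2.0/4.7 = 43% (41% to 44%).
- Half of each: 2.10/4.55 = 46%.
- Energy, either milk: (144 − 117)/144 = 27/144 = 19%.

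These are shares of milk intake at 180 ml/kg/d. While parenteral nutrition continues, the share of total protein is lower.

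**4. Late switch.** For an HDM-fed infant with an assumed fraction w of milk fortified, true protein = 2.2(1 − w) + 4.4w, against 2.2 recorded.
- w = 0.25: 0.55/2.75 = 20% missed.
- w = 0.50: 1.10/3.30 = 33% missed.
- w = 0.75: 1.65/3.85 = 43% missed.

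**5. Can fortifier be derived instead?** The fixed rate gives the amount once the fortified volume is known. That volume needs the infant's true arm and start date. The allocation field as listed does not give the arm. The start date is not listed, and the 100 and 150 ml/kg/d statements leave it open even in the fortified arm. For a switched infant the start date is individual and cannot be inferred from allocation at all.

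**6. Cell sizes after splitting.** Section 4.11.1 plans 66 scans. Five categories would average 66/5 ≈ 13 infants each.

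**The case against.** Several stronger readings are tempting, and the documents do not support them.

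- *The trial's main comparison is compromised.* It is not. The ITT regression and the ANOVA compare arms as randomised and keep fortified and unfortified HDM apart. The weakness lies in one supplementary model and in the intake data for Aim C.
- *Section 4.8.5 rests on the category analysis alone.* It names the per-protocol analysis first. That analysis could handle a switch if the switch is logged, perhaps under withdrawal information. However, neither the per-protocol set nor the content of that item is defined.
- *Aim C leaves out half the protein.* The documents do not say fortifier is excluded. Table 1 itself counts it, and the fixed rate allows partial derivation by arm. The 50% figure is a maximum, for an infant fed only fortified HDM.
- *Arm identity would be lost.* The two-level field matches the shorthand in 4.6. Section 4.4 speaks of three feeding arms, and allocation is generated centrally. The field needs correcting, but it does not show that the arm would be unknown.
- *Fortifier is the largest nutritional difference between arms.* Unfortified HDM and PTF differ by 2.5 g of protein, more than the 2.0 to 2.2 g that fortifier adds.

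Splitting the categories also has a real drawback. Switched infants are selected for poor weight gain, so placing them by fortified exposure puts slow growers into fortified groups. That is confounding by indication. It limits what the model can show, but it does not make milk-source-only categories able to show a switch.

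**Conclusion.** The concern holds in a limited form. As written, the intake categories cannot show a switch to fortifier, so one of the two analyses named in 4.8.5 cannot do its job, and *predominantly HDM* pools two randomised arms that differ twofold in protein. The listed CRF items do not allow individual fortifier exposure to be reliably rebuilt.

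For Aim C the consequence is conditional. If fortifier is neither recorded nor derived, milk protein in fortified infants could be understated by up to 43% to 50% at 180 ml/kg/d, and by about 20% to 43% for an HDM-fed infant fortified for a quarter to three quarters of intake. This assumes Table 1 composition and intake calculated from the listed volumes and bottle labels alone. The late-switch fractions are illustrative.

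The randomised ITT comparison is not affected. This is a repair to a secondary analysis and its data, and it should be made before the data are collected.

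**What to change.** - **4.9.3:** make the allocation field three-level.
- **4.9.5:** add fortifier start and stop dates and the daily volume fortified, separately for MOM and HDM.
- **Aim C:** state that fortifier is included in the intake calculation, and how.
- **4.11.2:** split the human-milk categories by fortification, giving unfortified MOM, fortified MOM, unfortified HDM, fortified HDM and PTF. If cells are too small, keep the milk-source categories and add the proportion of milk volume fortified as a covariate. State the threshold at which one milk predominates. Label the model exploratory and non-randomised, and note the confounding by indication for switched infants.
- **4.8.5 and 4.11.2:** define how the per-protocol analysis treats switched infants.
- **4.8.2, 4.8.4 and the protocol summary:** reconcile the enteral volume at which fortification starts, since the conflict prevents deriving the start date from volumes.

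The cost is a few sentences and a small number of CRF fields. Staff must enter the fortified volume daily, and the documents do not say from which source record. The statistical cost is thin cells of about 13 infants on average, which is why the covariate is offered as an alternative.
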